Intracellular detection of IFN-alpha and TNF-alpha cytokines in plasmacytoid dendritic cells: PBMC cells will be stimulated with TLR-7 and TLR-9 agonists, imiquimod (5 µg/mL) and CpG-A ODN 2216 (5 µM) for 5 hours at 37°C. After 3 hours of stimulation, Brefeldin A will be added to induce the accumulation of cytokines in the endoplasmic reticulum by its inhibitory action on intracellular protein transport to the Golgi complex. Phenotypic cell characterization (PBMC) and intracellular detection of cytokines will be performed by sequential membrane marking and intracellularly using specific monoclonal antibodies labeled with fluorochromes followed by evaluation by flow cytometry (Sacre et al., 2012).

WITHDRAWALS

It doesn't apply.

ORIGINALITY WITH IMPACT

Healthcare

To date, there is no study that has evaluated blood and salivary levels of hydroxychloroquine (HCQ) and its predictive value for disease activity in JSLE and adult lupus nephritis.

The expected impact with the availability of this technique in clinical practice is an improvement in therapeutic adherence and an earlier intervention with reduction of outbreaks of disease activity. The use of saliva as an alternative to this monitoring would provide a less invasive technique for this process.

ADVANCES IN MECHANISMS

The expected progress is a better understanding of the mechanism of action of HCQ on TLR-7-9, previously suggested as possible therapeutic targets for the disease.

STATISTICAL PLAN

SAMPLE SIZE

The sample size was calculated based on the HCQ levels observed in the study by Costedoat-Chalumeau et al., 2006, in patients with SLE and assuming: 95% confidence interval, α error of 5%; power of 80%; mean HCQ concentration in active patients: 694 ± 448 ng/mL; mean HCQ concentration in inactive patients: 1079 ± 526 ng/mL; aggregate standard deviation: 532 ng/mL and loss: 10%.

For the SLE group with nephritis, 16% of SLE patients in our outpatient clinic present active renal disease, then we expect 33 patients with renal activity out of the 206 patients which will be included.

For the JSLE group, 34% of our outpatient clinic patients present active, then 35 with disease activity are expected out of a total number of 103 patients to be included statistical analysis. The groups of patients with and without disease activity will be compared for categorical variables by Fisher's exact test and, for quantitative variables, by student and mann-whitney t tests, when applicable.

TITLE OF THE

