
In addition, it is extremely important to evaluate whether the reduction of the weekly dose of HCQ after a long period of use of this therapy would be able to maintain inhibition of TLR-7 and -9.

Objectives primary:

- Compare the frequency of outbreaks of disease activity (SLE and jSLE) in patients using standard dose (HCQ 400 mg/day) vs. patients with reduced dose (HCQ 400 mg/3X week) and its correlation with blood and saliva levels of the drug. Secondary: - Compare frequency of retinopathy in patients using standard dose (HCQ 400 mg/day) vs. patients with reduced dose (HCQ 400 mg/3X week) and its correlation with HCQ blood levels.

- Verify a possible longitudinal correlation of HCQ concentrations with the production of interferon-alpha and TNF by plasmacytoid dendritic cells.

- Correlate blood and salivary levels of HCQ and its metabolites in patients with SLE and JSLE with adherence to this treatment.

- Correlate functional and structural damage of the retina, evaluated by central visual field examination (campimetry) and SD-OCT measurements, with segmentation of the outer layer of the retina (pigment epithelium).

- Establishment of a pharmacokinetic-pharmacodynamic model of hydroxychloroquine dose reduction in patients with SLE.

NUMBER OF INDIVIDUALS

Total number of patients required for the study= 256 (SLE and JSLE).

STUDY DESIGN

Randomized controlled prospective study of non-inferiority of one year of follow-up of patients with SLE and JSLE in remission with HCQ use (stable dose of 400 mg/day for at least five years).

Patients will be randomized into two groups: no daily dose reduction group (HCQ 400 mg/day) and reduction group (HCQ 400 mg/day - 3X week). Patients will be evaluated for the activity of the underlying disease in a "blind" way. HCQ concentrations will be measured at the entrance, 6 months and 12 months after.

The groups will be compared for episodes of disease activity (clinical and laboratory parameters). The production of interferon-alpha and TNF by plasmacytoid dendritic cells will be evaluated in the same period in a subgroup of patients.

The following indexes will be used to assess disease activity:

- SLE and JSLE: SLEDAI-2K (Gladman et al., 2002) and active disease randomly defined as SLEDAI-2K \geq 6.

- Renal activity: BP, urine type I, protein and creatinine in an isolated urine sample, serum creatinine, C3, C4, anti-dsDNA, according to the recommendations of the ACR (Hahn et al., 2012).

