ADVANCES IN MECHANISMS Advances in understanding the role of cutaneous HCQ deposes acquired after prolonged previous treatment in maintaining drug-induced TLRs-7 and -9 inhibition would justify reducing the therapeutic dose based on the drug's immunomodulatory mechanisms of action.

SAMPLE SIZE

The sample size was calculated based on the difference in Reactivation of SLE/SJS in one year after the removal or maintenance of hydroxychloroquine, as observed in the study by Tsakonas et al., 1998 and assuming: 95% confidence interval, α error of 5%; power of 80%; expected success rate after 1 year in the group that kept HCQ at the standard dose (Tsakonas et al., 1998)- 84%; expected success rate after 1 year in the group that fully removes HCQ (Tsakonas et al., 1998)- 59%; no-inferiority margin- 50% of the difference between maintaining chloroquine or removing it completely, i.e., delta of 12%; losses- 10%; n in each group- 128; total number of patients to be recruited: 256 (for SLE/JSLE).

statistical analysis The comparison of the risk of inflammatory activity of the disease in patients using standard dose (HCQ 400 mg/day) vs. patients with reduced dose (HCQ 400mg/day - 3X week) will be made through a survival curve by the log-rank test. The categorical variables will be evaluated by fisher's exact or chi-square test and quantitative variables by student and mann-whitney t tests, when applicable.

TITLE OF THE SUBPROJECT 1C

Prospective study of the pharmacokinetics of hydroxychloroquine in patients with Systemic Lupus Erythematosus using attack dose diseases SLE and JSLE.

Justification

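### Subproject 1B pools adult and juvenile lupus with no named stratification or adjustment and gives no interval to set against its 12-point margin; a stratified risk difference would supply the interval and a little precision

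*Combined protocol and SAP*

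**What the plan says.** Subproject 1B, under its number of individuals, gives a single total for both diseases: "Total number of patients required for the study= 256 (SLE and JSLE". The sample-size paragraph repeats it: "losses- 10%; n in each group- 128; total number of patients to be recruited: 256 (for SLE/JSLE". It uses one expected one-year success rate, 84% on the standard dose, for the two diseases together. The margin is half the difference from the 59% expected after full withdrawal: "removing it completely, i.e., delta of 12" percentage points.

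The study design section says that patients are randomised into two groups. It describes no allocation method, blocking or strata. The statistical analysis paragraph says that the comparison of disease activity between arms "will be made through a survival curve by the log-rank test". It names no stratification, covariate adjustment or confidence interval. The design section does list many clinical variables, but for comparing patients with active and inactive disease, not for adjusting the comparison of arms.

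Subproject 1A treats the diseases separately. It recruits 206 SLE and 103 JSLE patients, and it studies renal activity in adults and overall activity in juveniles. Its sample-size section gives 16% of adult clinic patients with active renal disease. For JSLE it says "34% of our outpatient clinic patients present active".

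**The concern.** Disease group is known at entry and may be related to the risk of reactivation. If it is, and one arm receives more juvenile patients by chance, the crude arm difference moves for a reason unrelated to dose. An unadjusted analysis leaves that variation in the comparison and loses some precision. The sample size is set at 80% power with no stated reserve beyond 10% losses.

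The planned log-rank test also asks whether the two curves are equal, whereas the design asks whether the reduced schedule is worse by less than 12 points. A non-significant log-rank result would not answer that. 1B also presents itself as showing safety in both SLE and JSLE, yet it plans no result by group.

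**Working it through.** **Inputs from 1B's sample-size paragraph.** Success 84%, so reactivation 16%; margin 12 points; 128 per arm; losses 10%; and "95% confidence interval, α error of 5%; power of 80"%.

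**Assumptions, because 1B gives no figure.** Juvenile share f from 10% to 50% (1A's share is 103/309 = 33%). Gap in one-year reactivation of 18 points, which is 34 − 16 from 1A taken at face value, for scale only.

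**The plan's own number.** n per arm = (z₁₋α + z₀.₈₀)² × 2 × 0.84 × 0.16 / 0.12².
- One-sided α 0.05: (1.645 + 0.842)² × 0.2688 / 0.0144 = 115.4, so 116. Adding 10% gives 127.6, so 128, which is the plan's figure. Dividing by 0.9 gives 129.
- One-sided α 0.025, which matches a two-sided 95% interval: 147, or 164 after dividing by 0.9. This does not reproduce 128.

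**Standard error of the arm difference.** √(2 × 0.84 × 0.16 / 128) = 4.6 points. With 115 evaluable per arm (128 × 0.9) it is 4.8 points.

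**Chance imbalance.** The SD of the between-arm difference in juvenile share is √(f(1−f) × 2/128) × √(256/255). Multiplying by 0.18 gives the SD of the shift in the arm difference. At f = 1/3 this is 5.9 × 0.18 = 1.06 points, with a 95% range of 1.96 × 1.06 = ±2.1.

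**Simulation.** 100,000 runs per scenario, 115 evaluable per arm, overall reactivation held at 16%, an 18-point gap, and the same risk difference in both groups. Non-inferiority is concluded when the upper one-sided 95% limit for the excess in reactivation is below 12 points. The comparison is an unadjusted risk difference against a Mantel-Haenszel one. The log-rank test itself was not simulated, because it does not test the margin.

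| JSLE share | SD of imbalance (points) | SD of shift (points) | 95% range (points) | Power, unadjusted → stratified | Type I error, unadjusted → stratified |
|---|---|---|---|---|---|
| 10% | 3.8 | 0.68 | ±1.3 | 79.9% → 81.0% | 0.051 → 0.052 |
| 20% | 5.0 | 0.90 | ±1.8 | 79.9% → 81.5% | 0.051 → 0.054 |
| 33% | 5.9 | 1.06 | ±2.1 | 80.2% → 82.3% | 0.051 → 0.053 |
| 50% | 6.3 | 1.13 | ±2.2 | 79.9% → 82.1% | 0.050 → 0.052 |

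At one-sided 0.025, power rises from about 70% to between 72% and 73%.

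**Reading the size.**
- At f = 1/3 the between-group variance is (1/3)(2/3)(0.18²) = 0.0072, out of 0.16 × 0.84 = 0.134, or about 5%.
- The shift scales with the gap. Halving the gap to 9 points halves the 95% range to about ±0.7 to ±1.1, and with no gap it is zero.
- A 12-point shift would need an imbalance of 12/18 = 67 points in juvenile share.

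**The case against.** Three objections have force.

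- **The 16% and 34% in 1A cannot be subtracted.** A reader might infer from them that the plan expects juvenile patients to flare more often in 1B. The documents do not support this. The adult figure is active renal disease and the juvenile figure is any active disease. Both are prevalences in general clinic patients, whereas 1B follows patients in remission. At a one-third juvenile share they would give (2/3) × 16 + (1/3) × 34 = 22% overall, not 1B's 16%. This stands in full, and the 18-point gap serves only as an illustration.
- **Randomisation already deals with chance imbalance.** A reader might infer that pooling biases the comparison or raises the false-positive rate. It does neither: allocation is random, the ordinary standard error includes this variation, and the simulated type I error without stratification is 0.050 to 0.051. This also stands. What remains is that a borderline result could turn on avoidable noise.
- **The plan is silent on strata.** It does not say that allocation is unstratified. That is correct, so the point is that no factor is named.

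It can also be said that stratifying alone would not make a log-rank test address the margin. That is true, and it is why the change below concerns the effect measure and its interval as well as the strata.

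**Conclusion.** The point holds as a minor one. 1B pools two diseases, names no stratification or adjustment, and specifies no interval to set against its margin. Under the assumed gap, the loss is one of precision: the shift from imbalance has an SD of about 1 point against a standard error of 4.6. Stratifying does not materially change the required sample size. The gain would be smaller with a smaller gap and nil with none.

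The lack of an interval for the margin does not depend on the assumed gap or share. It follows from the analysis paragraph alone, and it is the stronger reason for the change.

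**What to change.** - If allocation has not begun, use separate lists for SLE and JSLE.
- In any case, before analysis, make the primary analysis a Mantel-Haenszel risk difference in one-year reactivation, stratified by SLE versus JSLE, and compare its confidence interval with the 12-point margin.
- State the interval's level. The 128 per arm matches one-sided 0.05. With a two-sided 95% interval, 115 evaluable per arm gives about 70% power under the plan's own assumptions.
- State how patients lost before one year enter the risk difference, since the plan allows for 10% losses.
- Keep a stratified log-rank or Cox analysis as supportive, and report each group descriptively.

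The cost is small but not nil: a second allocation list, a stated rule for who counts as JSLE (1B's inclusion criteria give no age cut-off), and a simulated type I error of 0.052 to 0.054 against a nominal 0.05. No extra patients are needed for the stratification itself.

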Adherence will be assessed by the MASRI questionnaire applied by a pharmacist not directly involved in patient care (Koneru et al., 2007).

The following clinical, laboratory and treatment data will be evaluated in the groups (active disease and inactive disease): age, sex, race, weight, height, BMI, ideal weight; disease time, time of HCQ use, adherence to treatment; smoking; use and dose of prednisone, methotrexate, azathioprine, mycophenolate mofetil, cyclophosphamide, non-hormonal anti-inflammatory drugs; urinary protein/creatinine ratio; serum creatinine; blood concentrations of HCQ by HPLC; specific adverse events.

- Complete ophthalmologic assessment (at the entrance and at the end of the study), including campimetry and SD-OCT measurements, with segmentation of the outer layer of the retina (pigmentary epithelium).

- The production of interferon-alpha and TNF-alpha by plasmacytoid dendritic cells will be evaluated in vitro using mononuclear cell preparations isolated from peripheral blood from a random sample of the same number of consecutive patients with active and inactive SLE. The cells will be stimulated with the TLR-9 agonist, Oligodeoxynucleotide S CpG (ODN CpG-A)-2216 and with the TLR-7 agonist, imiquimod. The percentage of monocytes, B cells, dendritic cells and natural killers (NK) in the PBMC fraction will be determined by the phenotypic characterization of these cell subpopulations by flow cytometry using monoclonal fluorochrome-conjugated antibodies. Intracellular detection of IFN-alpha and TNF-alpha in plasmacytoid dendritic cells will also be performed by flow cytometry and specific monoclonal antibodies (Sacre et al., 2012).

- Establishment of a pharmacokinetic-pharmacodynamic model of hydroxychloroquine use with two groups of 5 patients: one with 5mg/kg/day daily and another 5mg/Kg/day 3 times a week. On inclusion both will be on hydroxychloroquine use for at least 6 months and should have the stable level of the drug (> 1000ng/mL).

Outcomes: assessment on days 0 and 120 days.

a) Worsens no SLEDAI -2K. Change in SLEDAI-2K evaluating activity criteria from 0-105 in 9 organs and 24 items (clinical and laboratorial). The increase represents clinical/laboratory worsening of the disease.

b) Cytokine measurement. Plasma levels of TNF- α and IFN-1 will be determined by Luminex MAP (EMD Millipore Corporation®). Plasma samples will be stored at -80oC until use.

TARGET POPULATION

Inclusion criteria:

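### Subproject 1B does not count or compare by arm increases in prednisone or immunosuppressants, so worsening treated before it is recorded can pass as success in a non-inferiority trial

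*Combined protocol and SAP*

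**What the plan says.** All references are to the Combined protocol and SAP.

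- **Design (Subproject 1B, Study design).** "Randomized controlled prospective study of non-inferiority of one year of follow-up of patients with SLE and JSLE in remission with HCQ use". Daily dosing is compared with dosing three times a week.
- **Event (same section).** "The groups will be compared for episodes of disease activity (clinical and laboratory parameters"). Two indices follow: SLEDAI-2K, with "active disease randomly defined as SLEDAI-2K" of 6 or more, and a set of renal measures with no numeric threshold. 1B gives no timetable for SLEDAI-2K; Subproject 1A gives one of every three months.
- **Blinding (same section).** "Patients will be evaluated for the activity of the underlying disease in a 'blind' way". Neither a placebo nor any masking of patients or treating clinicians is described.
- **Other lupus drugs (same section).** The recorded data include "use and dose of prednisone, methotrexate, azathioprine, mycophenolate mofetil, cyclophosphamide, non-hormonal anti-inflammatory drugs". They are to be evaluated in patients with active and inactive disease, not by randomised arm.
- **Handling of changes.** No 1B section holds these drugs stable, counts an increase as an event, censors at an increase or plans a sensitivity analysis. Retinopathy is the only reason given under Withdrawals, and a log-rank test is the only primary analysis. By contrast, Project 2 (Study design) says that other lupus drugs are to be maintained.

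**The concern.** A lupus patient who starts to worsen may be given more prednisone or immunosuppressant. If that happens before an assessment records activity, the score may never reach 6 and the patient is counted as still in remission. The worsening leaves no trace in the primary comparison.

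In a superiority trial this would mostly cost power. Here the claim rests on the difference being small, so anything that removes events tends to favour the claim. 1B is meant to show that the dose can be reduced safely, without more flares. If control in the reduced arm was bought with more steroid or immunosuppressant, the primary analysis would not show it, and no other planned analysis compares those drugs by arm.

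**Working it through.** **1. Reproduce the plan's sample size.** Inputs from 1B, Sample size: 84% success on the standard dose; "59%; no-inferiority margin- 50% of the difference between maintaining chloroquine" or removing it, stated as 12 points; power 80%; alpha 5%; losses 10%. Equal success in both arms is an assumption, as the plan gives no rate for the reduced arm.

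n = (z for alpha + z for power)² × 2 × p(1 − p) / margin²

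= (1.645 + 0.842)² × 2 × 0.84 × 0.16 / 0.12², which rounds up to 116 evaluable per arm. Then 116 × 1.10 = 127.6, or 128 as stated. This needs alpha to be one-sided 5%; one-sided 2.5% gives 147 before losses. The stated size therefore reproduces, and the point does not rest on an arithmetic error.

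**2. Set the true rates at the margin.** Standard arm 16% (100 − 84); reduced arm 28% (16 + 12). Non-inferiority should then be declared only 5% of the time.

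**3. Hide a share of events.** Let hS and hR be the shares of true events treated before they are recorded in the standard and reduced arms. These are assumed, because the documents give no such figure.

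- Observed rates: fS = 0.16(1 − hS), fR = 0.28(1 − hR); d = fR − fS
- SE = √[(fS(1 − fS) + fR(1 − fR)) / 116]
- Probability of declaring non-inferiority = Φ[(0.12 − d)/SE − 1.645]

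Example, 20% hidden in both arms: fS = 0.128, fR = 0.224, d = 0.096, SE = √[(0.1116 + 0.1738)/116] = 0.0496. Then Φ(0.024/0.0496 − 1.645) = Φ(−1.16) = 12.3%.

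| Hidden: standard / reduced | Observed difference (points) | False non-inferiority risk |
|---|---|---|
| 0 / 0 | 12.0 | 5.0% |
| 10% / 10% | 10.8 | 7.9% |
| 20% / 20% | 9.6 | 12.3% |
| 30% / 30% | 8.4 | 18.9% |
| 10% / 30% | 5.2 | 39.6% |
| 30% / 10% | 14.0 | 2.0% |

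A binomial simulation of the 0/0, 20/20, 30/30 and 10/30 rows gave 5.1%, 12.5%, 19.5% and 39.9%.

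**4. Where the direction turns.** The observed difference stays at 12 points when 0.28 × hR = 0.16 × hS, that is hS = 1.75 × hR. The bias runs against non-inferiority only if the hidden share in the standard arm exceeds 1.75 times that in the reduced arm.

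**5. Cost of counting escalation.** With equal true rates and 116 per arm, power is 80% at a 16% event rate. If counting escalation raises the common rate to 20%, 24% or 28%, power is 74%, 69% or 65%. Keeping 80% would need 138, 157 or 174 evaluable per arm.

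**The case against.** A reader might infer more than the documents support.

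- **That a flare is counted only through SLEDAI-2K.** Renal activity and unspecified clinical and laboratory parameters are also named, and flares are monitored under Safety. The event is under-defined rather than confined to one score. All these are still activity measures, so the gap remains.
- **That clinicians know the arm and may escalate freely.** The schedules differ visibly and no masking beyond the activity assessment is described, so knowledge of the arm is likely. The plan does not say the trial is open-label, and it does not state that escalation is permitted. Both readings rest on silence.
- **That the bias must favour the reduced dose.** Step 4 shows when it reverses. Patients known to be on less drug might also report more symptoms or be examined more often, which would find more events in that arm. Worsening already recorded still counts.
- **That an observed loss below 12 points means non-inferiority would be declared.** The confidence limit decides. In the 10%/30% case the upper limit at the expected difference is 5.2 + 1.645 × 4.92 = 13.3 points, so failing to show non-inferiority remains the likelier result.

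It can also be argued that activity alone, assessed blind, is a defensible primary event, and that adding a clinician's decision trades one bias for another. That stands, and it is why the remedy below leaves the primary event in place. It does not excuse having no analysis of escalation by arm.

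**Conclusion.** The point holds as a gap in 1B: increases in background lupus treatment are neither counted, restricted nor compared by randomised arm, so worsening treated before it is recorded would count as success. If the hidden share is equal in both arms or heavier in the reduced arm, the bias is towards non-inferiority. Equal hiding of 10% to 30% raises a 5% false-claim risk to between 8% and 19%, and 10% against 30% raises it to about 40%.

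These figures assume true rates exactly at the margin, 116 evaluable per arm and one-sided 5%. At one-sided 2.5% with the same 116, the equal-hiding risks are 4.2%, 7.0% and 11.6%, and the unequal case is 28%. The hidden shares are illustrative: with no escalation rate and no 1B timetable for SLEDAI-2K, the documents cannot fix the actual size. They do not support saying that the trial is biased towards its claim, only that the plan could not detect it if it were.

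**What to change.** Keep the blindly assessed activity event as primary and pre-specify two further analyses:

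1. A comparison by randomised arm of new or increased prednisone or immunosuppressant use for lupus activity.
2. A key sensitivity analysis of time to the first activity event or such escalation, reported as a one-year difference with its confidence limit set against the 12-point margin. A log-rank test alone does not show non-inferiority. State that a non-inferiority claim will be qualified if this analysis and the primary disagree.

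Record the date and reason of each change; the plan lists only use and dose. State also who is masked, when SLEDAI-2K is assessed in 1B and what counts as a renal event.

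The cost is a small amount of extra recording and some analysis text. There are two drawbacks. Escalation may be influenced by knowledge of the arm, probably against the reduced dose. The composite also has less power, about 74% if its event rate is 20%, so its failure to meet the margin should be read with that in mind. The documents do not give the event definition behind the margin, so its use for the composite should be justified. Nothing here sets a rule on when treatment is escalated; that is for the sponsor to state.

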- LES and jSLE (ACR criteria) (Hochberg, 1997);
- use of HCQ at a dose of 400 mg/day for at least 3 years.

Exclusion criteria:

- alcoholism;
- renal dialysis;
- concomitant infectious process;
- acute and chronic liver diseases;
- concomitant use of some drugs that interact with HCQ (cimetidine, antacids, digoxin, aminoglycosides, penicillin, neostigmine, pyridostigmine).

RELEVANT METHODS - Ophthalmological assessment: central visual field examination (campimetry) and SD-OCT measurements, with segmentation of the outer layer of the retina (pigmentary epithelium).

- Blood levels of HCQ will be determined by HPLC MS/MS (Munster et al., 2002).

- Pharmacokinetic analysis: The pharmacokinetic parameters of hydroxychloroquine will be calculated in the 24 h dose range based on the total plasma concentration versus time curves. The Winnonlin program, version 4.0 (PharsightCorp., Mountain View, California, USA) and the Non-linear mixed effect level (NONMEM) program will be employed. The area under the plasma concentration curve versus time will be calculated in the 24-h dose interval by the trapezoid method on days 0 and 120. The apparent total clearance (CIT/F) will be obtained through the equation: $CIT/F = Dose/AUC_{0-24}$. The apparent distribution volume (Vd/F) will be calculated by the standard software equation. The hydroxychloroquine-free concentration will be determined by the dosage in saliva. The PK-PD analysis will be performed using as pharmacokinetic parameters the total and free plasma concentrations of hydroxychloroquine and, as a pharmacodynamic parameter, we will use the clinical/laboratory indices obtained by the evaluation of SLEDAI-2K (American College of Rheumatology). The PK-PD model will be developed using the non-linear mixed effect level (NONMEM).

- Others, the same as described in subproject 1A.

Safety

Monitoring of outbreaks of inflammatory activity (flare) and identification of retinopathy.

WITHDRAWALS

Signs of retinopathy.

ORIGINALITY WITH IMPACT on

Healthcare

To date, there is no study demonstrating that the reduction of HCQ dosage after tissue depot caused by a prolonged time of use of the drug can be safely performed in SLEJ and SLE, without increasing the number of outbreaks of inflammatory activity.

The expected care impact is a reduction of severe ophthalmologic event with the reduction of the HCQ dose and the expansion of the time of use of the drug that has a direct impact on the control of disease activity.

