- Evaluate the clinical/laboratory response and adverse events in both groups.
- Verify a possible correlation of HCQ concentrations in blood and saliva with interferon-alpha and TNF production levels by plasmacytoid dendritic cells and disease activity parameters.
- Correlate blood and salivary levels of HCQ and its metabolites in Patients with SLE with adherence to this treatment.

NUMBER OF INDIVIDUALS

Total patients needed for the study = 96 (SLE).

STUDY DESIGN

Prospective randomized study controlled for a period of six months of patients with SLE who will start the use of HCQ.

Patients will be randomized randomly into two groups: traditional group - without increasing the daily dose (HCQ 400 mg/day); attack dose group - with increased daily dose (HCQ 800 mg/day for 6 months). Patients will be evaluated for the activity of the underlying disease in a "blind" way. HCQ concentrations will be assessed at the entrance and at the end of the study.

The groups will be compared for episodes of disease activity (clinical and laboratory parameters), inflammatory cytokines, and expression of TLR-7 and TLR-9 receptors.

Blood concentrations of HCQ and metabolites will be determined in both groups by HPLC (Munster et al., 2002).

The following indexes will be used to assess disease activity:

- SLE: SLEDAI-2K (Gladman et al., 2002) and active disease randomly defined as SLEDAI-2K \geq 6.

- Renal activity: BP, urine type I, protein and creatinine in an isolated urine sample, serum creatinine, C3, C4, anti-dsDNA, according to the ACR Guidelines (Hahn et al., 2012).

Adherence will be assessed by the MASRI questionnaire applied by a pharmacist not directly involved in patient care (Koneru et al., 2007).

The following clinical, laboratory and treatment data will be evaluated in the groups (traditional dose and attack dose): age, sex, race, weight, height, BMI, ideal weight; disease time, time of HCQ use, adherence to treatment; smoking; use and dose of prednisone, methotrexate, azathioprine, mycophenolate mofetil, cyclophosphamide, non-hormonal anti-inflammatory drugs; urinary protein/creatinine ratio; serum creatinine; HCQ blood concentrations by HPLC MS/MS; general- gastrointestinal and cutaneous adverse events.

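### Subproject 1B plans its data list, including HCQ levels and specific adverse events, by active v inactive disease, and states no comparison of these items by randomised arm

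*Combined protocol and SAP*

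**What the plan says.** Subproject 1B of the combined protocol and SAP is a one-year randomised non-inferiority trial in patients whom Study design describes as in remission. The allocation is: "Patients will be randomized into two groups: no daily dose reduction group (HCQ 400 mg/day) and reduction group (HCQ 400 mg/day - 3X week". Active disease is a SLEDAI-2K score of 6 or more.

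The same section introduces a list of data: "The following clinical, laboratory and treatment data will be evaluated in the groups (active disease and inactive disease". The list starts with demographics and disease duration, goes on through adherence, co-medication and renal measures, and ends with "blood concentrations of HCQ by HPLC; specific adverse events".

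Other parts of 1B do use the randomised arms. Directly after the allocation, Study design says: "The groups will be compared for episodes of disease activity (clinical and laboratory parameters". A secondary objective is to "Compare frequency of retinopathy in patients using standard dose (HCQ 400 mg/day) vs. patients with reduced dose (HCQ 400 mg/3X week". The statistical analysis paragraph says that the comparison of disease activity between the two doses "will be made through a survival curve by the log-rank test". The sentence after it assigns tests to categorical and quantitative variables and names no grouping. The Safety item reads: "Monitoring of outbreaks of inflammatory activity (flare) and identification of retinopathy".

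Subproject 1C, also randomised, has a near-identical list with a different grouping: "The following clinical, laboratory and treatment data will be evaluated in the groups (traditional dose and attack dose".

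**The concern.** Patients enter in remission, so being active or inactive is a result that arises after randomisation, and it is the trial's own outcome. Grouping by it is not a comparison of the two schedules. It cannot show whether the arms were alike at baseline, because the groups do not exist at baseline.

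The gap matters more because 1B is a non-inferiority trial. If patients on the reduced schedule took more than allocated, or patients on the standard schedule took less, exposure in the arms would converge and the arms would tend to look alike. HCQ levels and adherence by arm are the direct evidence on whether two different schedules were delivered. Levels by flare status do not answer that question. A reader of a non-inferiority result would also expect adverse events by arm.

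**Working it through.** The point turns on what is stated, so the first step is to set the statements side by side.

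| Item | Where a grouping is stated | Grouping |
|---|---|---|
| Flare (1B) | Primary objective, Study design, statistical analysis | Randomised arm |
| Retinopathy (1B) | Secondary objective | Randomised arm |
| Baseline characteristics, co-medication, adherence, renal measures (1B) | Data list in Study design | Active v inactive |
| HCQ blood levels (1B) | Data list in Study design; the objectives speak only of correlation | Active v inactive |
| Specific adverse events (1B) | Data list in Study design | Active v inactive |
| Other categorical and quantitative tests (1B) | Statistical analysis | None named |
| Similar data list (1C) | Study design | Randomised arm |

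HCQ is measured at entry, 6 and 12 months, but no comparison of these levels by arm is stated for the trial population. The one place where concentrations are organised by schedule is the pharmacokinetic-pharmacodynamic model, with two groups of 5 patients assessed on days 0 and 120. That is a modelling exercise in 10 patients and does not describe exposure in the 256.

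The second step is an illustration of what the grouping does. The inputs from the Sample size section of 1B are 128 per group, 256 in total, 84% expected success on the standard dose and a margin of 12 points. The stated n reproduces with a one-sided 5% alpha and 80% power: (1.645 + 0.842)² × 2 × 0.84 × 0.16 / 0.12² = 115.4, so 116 per arm, and 116 × 1.10 = 127.6, so 128. The grouping question does not depend on this figure.

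The documents give no adverse-event rates. Assume an event in 10% of the standard arm and 5% of the reduced arm, independent of flare within each arm, and no losses.

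*Same flare rate in both arms (16%).*
- Active: 128 × 0.16 + 128 × 0.16 = 20.48 + 20.48 = 40.96, about 41. Inactive: 256 − 41 = 215. Each group is half from each arm.
- Event rate in either group: 0.5 × 10% + 0.5 × 5% = 7.5%. The 5-point difference between arms becomes 0.

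*Reduced arm at the margin (84% − 12 points = 72% success, 28% flare).*
- Active: 128 × 0.16 + 128 × 0.28 = 20.48 + 35.84 = 56.32. Inactive: 256 − 56.32 = 199.68.
- Event rate, active: (20.48 × 0.10 + 35.84 × 0.05) / 56.32 = 3.84 / 56.32 = 6.8%.
- Event rate, inactive: (107.52 × 0.10 + 92.16 × 0.05) / 199.68 = 15.36 / 199.68 = 7.7%.
- The gap is about 1 point in place of 5, and it is not an arm contrast.

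**The case against.** The strongest reply is that the sentence is a list of data in Study design and does not exclude other analyses. It does not say that these are the only groups. In the statistical analysis paragraph, the sentence on categorical and quantitative tests follows one that names standard v reduced dose, so those tests could be read as by arm. That reading is possible. But the test sentence names no grouping, while the data list does, so the only explicit rule for these items is the outcome grouping.

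Second, grouping HCQ levels by disease activity serves a stated aim: the primary objective includes the correlation of outbreaks with blood and saliva levels. This stands. The active v inactive analysis is legitimate and should stay; what is missing is the comparison by arm beside it.

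Third, a reader might infer that the trial's safety data as a whole are grouped by outcome. The documents do not support that. The Safety item of 1B names flare and retinopathy, and both are compared by randomised dose. The specific adverse events in the list may even be mainly retinopathy, since it is the only adverse drug effect that 1B names. The protocol does not define the term, so how many other events are affected is uncertain.

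Fourth, the illustrative split applies the standard-arm success rate to both arms and ignores the stated 10% losses. That is correct, and the split measures no bias.

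**Conclusion.** The point holds for the listed items. In a randomised trial, baseline characteristics, co-medication, adherence, renal measures, HCQ levels and specific adverse events are planned by a post-randomisation outcome, and no comparison by arm is stated for them. Followed as written, the list gives no arm contrast for baseline balance, adherence, exposure or adverse events other than retinopathy. The wording should be changed, because these contrasts are needed to interpret a non-inferiority result.

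It would be too strong to say that the randomisation is discarded: the primary comparison of disease activity is by arm. A reader might also conclude that the phrase was carried over from cross-sectional 1A, which compares patients with and without disease activity. That is plausible, but 1A contains no such data-list sentence and the documents do not say so. The point does not need it.

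The conclusion rests on the statement in Study design that patients are in remission at entry. The 41 v 215 split is illustrative only, since it assumes 84% success in both arms and no losses. The 10% and 5% event rates, and their independence of flare, are assumptions that show how an arm difference can be hidden. They do not predict its size.

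**What to change.** Change the data-list sentence in the Study design of 1B so that these data are summarised and compared by randomised arm (standard dose v reduced dose): baseline characteristics and co-medication, adherence, renal measures, HCQ levels at entry, 6 and 12 months, and all adverse events. Add the same grouping to the sentence on categorical and quantitative tests in the statistical analysis paragraph. Keep active v inactive disease as an additional exploratory analysis, tied to the stated correlation of HCQ levels with disease activity.

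The cost is a wording change in two sentences and one more set of tables. It needs no new data, visits or patients, and it leaves the primary analysis and the sample size as they are.
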